1	21 st March 2018	References to mineralocorticoid receptor antagonists (MRAs) updated in the following sections: 3. List of definitions (page 8), 4. Study synopsis (pages 9 and 11), 6. Background (page 15), 7. Aim and objectives (page 16), 9. Study design and methodology (pages 20 and 23).	Only spironolactone was previously included in the protocol but data on eplerenone will also be collected in the study.
2	21 st March 2018	Removal of exclusion criteria for "Received dialysis during the observation period". The following sections have been updated: 4. Study synopsis (page 11) 9. Study design and methodology (page 18).	Although very few patients with CKD stage 3 or 4 (study population of interest) will receive dialysis, excluding these patients may introduce bias and therefore they should not be excluded from the study.
3	21 st March 2018	Secton 17. Study timelines updated (page 31).	Updated as timelines for study activities (but not study completion date) have changed since the last version of the protocol in December 2017.

6. Background and rationale

It is estimated that approximately 6% of the population of England aged 16 years or older have (diagnosed or undiagnosed) chronic kidney disease (CKD) stage 3 to 5¹. Renin–angiotensin–aldosterone system inhibitors (RAASi) are commonly prescribed to patients with CKD, with or without heart failure (HF) and with or without diabetes mellitus. RAASi include the following drug types: angiotensin converting enzyme inhibitors (ACEi) and angiotensin receptor blockers (ARBs).

RAASi are used to delay disease progression (e.g. end-stage renal failure) and to prevent major cardiac events. As such, they can maintain/improve and prolong patients' quality of life. The introduction and maintenance of RAASi treatment is well established as part of recommended treatment pathways for CKD and HF^{2–4}. However, patients treated with RAASi are at risk of elevated serum potassium levels (hyperkalaemia), through impaired renal function and/or side effect of the drugs. As hyperkalaemia can be a serious medical emergency, leading to organ failure and resulting in death, patients often do not achieve the target doses that are required for optimal clinical benefit due to clinician concerns about potential, or actual episodes of, hyperkalaemia^{5–7}. Patients with HF are typically also treated with a mineralocorticoid receptor antagonist (MRA), such as spironolactone or eplerenone.

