9.5.2 Secondary endpoints

The following endpoints will also be measured:

Prescribing modalities, including concomitant prescribing

- Length of time on maximum tolerated daily dose of RAASi
- Proportion of patients with HF who receive RAASi and MRA

- Maximum tolerated daily dose of MRA achieved in patients with HF
- Length of time on maximum tolerated daily dose of MRA in patients with HF
- Distribution of other drugs concomitantly prescribed for CKD and/or HF in patients treated with RAASi, by drug type

Clinical outcomes

- Proportion of patients with elevated serum potassium level (>5.1 mmol/L, >5.5 mmol/L or >6.0 mmol/L) during the observation period
- Number of episodes per patient with elevated serum potassium level (>5.1 mmol/L, >5.5 mmol/L or >6.0 mmol/L)
- Change in mean serum potassium level (from index date to last result during observation period)
- Change in mean serum creatinine level (from index date to last result during observation period)
- Change in mean urine protein level (from index date to last result during observation period)
- Change in mean blood pressure level (from index date to last result during observation period)
- Proportion of patients who stop RAASi treatment at least once during the observation period
- Reason(s) for changing RAASi dose or stopping RAASi treatment, where relevant

The following patient characteristics will also be included in analyses:

- Age at index event
- Sex
- Ethnicity
- HF status
- Comorbidities documented at baseline
- Length of time since diagnosis of CKD (and HF and/or T2DM, if relevant) at index event
- eGFR at baseline

- LVEF at baseline, if diagnosed with HF

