9.5.3 Variables to be collected

The variables to be collected in this study are shown in Table 2.

Table 2 Study variables

Data Item	Required detail	Time point(s)	Data source(s)
Date of birth	MM/YYYY	Index event	Hospital medical record
Gender	F, M	Index event	Hospital medical record
Ethnicity	Based on categories recommended by Office for National Statistics: White, Mixed / Multiple ethnic groups, Asian / Asian British, Black / African / Caribbean / Black British, Other ethnic group	Baseline	Hospital medical record
Date of CKD diagnosis	MM/YYYY	Baseline	Hospital medical record
Date of HF diagnosis, if relevant	MM/YYYY	Baseline	Hospital medical record
Date of T2DM diagnosis, if relevant	MM/YYYY	Baseline	Hospital medical record
Comorbidities	Based on diseases and conditions recorded in medical record	Baseline	Hospital medical record
eGFR	Date of observation, rate	Baseline until end of	Hospital medical records,

		observation period	including primary care correspondence
LVEF	Date of observation, ejection fraction	Baseline until end of observation period	Hospital medical records, including primary care correspondence
Serum potassium	Date of observation, level	Index date until end of observation period	Hospital medical records, including primary care correspondence
Serum creatinine	Date of observation, level	Index date until end of observation period	Hospital medical records, including primary care correspondence
Urine protein (albumin:creatinine ratio, ACR or protein:creatinine ratio, PCR)	Date of observation, level, type of test	Index date until end of observation period	Hospital medical records, including primary care correspondence
Blood pressure	Date of observation, level	Index date until end of observation period	Hospital medical records, including primary care correspondence
RAASi prescriptions	Drug name, dose, start date	Index date until end of observation	Hospital medical records, including

		period	primary care correspondence
MRA prescriptions, if relevant	Drug name, dose, start date	Index date until end of observation period	Hospital medical records, including primary care correspondence
Concomitant medications for CKD and/or HF	Drug name, start date	Index date until end of observation period	Hospital medical records, including primary care correspondence
Change in RAASi treatment	Date of change, reason for dose change/stopping of treatment	Index date until end of observation period	Hospital medical records, including primary care correspondence

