Given the descriptive nature of this study, a preliminary estimation of the required sample size is expressed in terms of precision and not statistical power. It is expected that approximately 100 patients will be sufficient to generate reliable results, as determined by relatively narrow confidence intervals.

Table 3 Confidence limits for different sample sizes and mean doses of RAASi achieved

Mean dose (as % of target dose)	50 patients		100 patients		150 patients	
	LCL	UCL	LCL	UCL	LCL	UCL
90%	82%	98%	84%	96%	85%	95%
80%	72%	88%	75%	85%	76%	84%
70%	63%	77%	65%	75%	66%	74%
60%	54%	66%	56%	64%	57%	63%
50%	45%	55%	47%	53%	47%	53%
40%	34%	46%	36%	44%	37%	42%
30%	23%	37%	25%	35%	26%	32%

LCL – lower confidence limit

UCL – upper confidence limit

The table shows that the reliability of estimates for the mean dose of RAASi achieved (as a percentage of the target dose) improves when the study sample is increased from 50 to 100

patients. This is applicable for relatively small or large percentages of the target dose achieved. Reliability does not improve much more when the sample size is increased from 100 to 150 patients. Therefore, approximately 100 patients will be sufficient to generate reliable results for the primary endpoint. The number of patients in the study will be allocated as follows: 50% (approximately n=50) with CKD and HF and 50% (approximately n=50) with CKD and T2DM. This distribution includes patients with all three conditions: CKD, HF and T2DM.

12. Statistical analysis

Analyses will be performed by pH Associates. Data from all centres will be pooled for analysis. Distributions and descriptive statistics of central tendency (medians and arithmetic means) and dispersion (standard deviation, interquartile range) will be presented for quantitative variables wherever possible. Categorical variables will be described with frequencies and percentages. Ordinal variables will also have medians and interquartile ranges described. 95% confidence intervals will be presented for estimates of proportions and means of distributions.

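### The MRA duration endpoint is not reliably measurable when MRA is stopped, because Table 2 collects no MRA change or stop date

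*Protocol*

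**What the plan says.** Section 9.5.2 lists two duration endpoints among the secondary endpoints: "Length of time on maximum tolerated daily dose of RAASi" and "Length of time on maximum tolerated daily dose of MRA in patients with HF". Section 3 defines the maximum tolerated dose, for RAASi and MRA alike, as the highest recorded in the observation period, and sets that period at 12 months from the index event.

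Table 2 in Section 9.5.3 is the protocol's list of variables to collect. Three of its rows matter here:

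- RAASi prescriptions: "Drug name, dose, start date".
- "MRA prescriptions, if relevant": the same three details, and nothing more.
- "Change in RAASi treatment": "Date of change, reason for dose change/stopping of treatment".

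There is no matching change row for MRA. Section 6 states the scope of the term: "RAASi include the following drug types: angiotensin converting enzyme inhibitors (ACEi) and angiotensin receptor blockers (ARBs". Section 3 and Table 2 likewise name MRA separately from RAASi.

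**The concern.** A duration needs a start and an end. For RAASi the protocol collects both: prescriptions give the starts, and the change row gives dated changes and stops. For MRA it collects only starts. The RAASi prescription row has the same wording as the MRA row, yet the protocol adds a change row for RAASi. It therefore does not treat start dates alone as enough for RAASi, but leaves MRA with nothing else.

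Stopping matters in this population. Section 6 says that MRAs add to the risk of hyperkalaemia and that patients with CKD and HF may receive a below-target MRA dose or none. If MRA stops go undated, the endpoint can overstate how long patients stay on their highest dose. The gap would not show up as missing data either, because there is no field to be left blank or marked as not known under Section 12.1.

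**Working it through.** The protocol gives no expected value, precision or stopping rate for either duration endpoint (Table 3 concerns mean RAASi dose only), so there is no figure to reproduce. The check compares the endpoint with the data items and then illustrates the size.

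**Step 1. What ends a spell on the maximum MRA dose, and is it dated?**

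| How the spell ends | Dated by Table 2? |
|---|---|
| Step-down to a lower MRA dose | Yes, by the next MRA start date |
| Switch to the other MRA | Yes, by the next MRA start date |
| Stop, no later MRA prescription | No |
| Still on the dose at month 12 | No end within the window |

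The last two rows produce identical records: a final MRA entry with a start date and nothing after it.

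**Step 2. Size if open spells are run to month 12.** The protocol does not say how open spells are closed, so this rule is an assumption. Let s be the month in which the maximum dose is reached, w = 12 − s the remaining window, and q the fraction who stop with no later MRA prescription. Assume that stops are spread uniformly over w and that everyone else stays on the dose to month 12.

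- True in-window mean: (1 − q)·w + q·w/2 = w·(1 − q/2).
- Mean computed without stop dates: w.
- Relative overstatement: 1/(1 − q/2) − 1 = q/(2 − q), which does not depend on w.

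| q (assumed) | True mean, w = 12 | True mean, w = 6 | Overstatement |
|---|---|---|---|
| 10% | 11.40 months | 5.70 months | 5% |
| 20% | 10.80 months | 5.40 months | 11% |
| 30% | 10.20 months | 5.10 months | 18% |
| 50% | 9.00 months | 4.50 months | 33% |

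In months, the error is q·w/2. That runs from 0.6 (q = 10%) to 3.0 (q = 50%) if the maximum dose is reached at index, and from 0.3 to 1.5 if it is reached at month 6.

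**Step 3. Would another rule for open spells help?** Dropping them as incomplete, in the spirit of the complete-case rule in Section 12.1, would also drop every patient who stayed on the dose to month 12. Neither rule separates the two kinds of patient.

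**The case against.** Four points can be made on the other side.

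*The endpoint is partly measurable.* A reader might infer that MRA duration cannot be measured at all, or that it is overstated for everyone who stops. The documents do not support that. MRA prescriptions are collected with dose and start date to the end of the observation period, so step-downs and switches are dated. A patient who steps down and then stops has a dated end to the maximum-dose spell. The fault is confined to stops taken directly from the maximum dose with no later MRA prescription.

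*The scope is small.* This is one secondary endpoint, for MRA users within an HF group of about 50 (Section 11). RAASi changes and stops are dated, so this gap does not touch the primary endpoint or RAASi duration. That stands, and it limits the weight of the point.

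*The statistical analysis plan could settle it.* It can fix a rule for open spells, but it cannot supply a date that was not abstracted. This part of the objection fails.

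*The 12-month cut.* A reader might also infer that both durations are truncated at month 12 and then wrongly treated as complete, since Section 12 says that "descriptive statistics of central tendency (medians and arithmetic means) and dispersion (standard deviation, interquartile range) will be presented" and names no time-to-event method. The protocol never calls them complete durations. Section 9.5 ties the endpoints to the observation period, Section 3 fixes that at 12 months, and Section 9.2.1 requires at least 12 months of follow-up data. Time on the maximum dose within that window is a valid quantity, fully observed for RAASi, and means or medians of it are legitimate. How patients still on the dose at month 12 are handled may be left to the statistical analysis plan.

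**Conclusion.** The point holds in a limited form. The protocol sets an MRA duration endpoint but does not collect what is needed to tell a patient who stops MRA from one who continues to month 12. Nothing elsewhere in the document closes the gap.

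The size depends on a stopping rate that the protocol does not give. For assumed stop fractions of 10% to 50%, the mean in-window duration is overstated by about 5% to 33%. This rests on running open spells to month 12, uniform stop times, and no step-downs among the remaining patients. Stops clustered early would enlarge the error, and stops clustered late would shrink it.

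The documents do not support the wider readings, that the endpoint is wholly unmeasurable or that a survival analysis is required.

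**What to change.** Extend the existing change row in Table 2 and the eDCF so that it covers RAASi or MRA treatment, with the date of each change or stop and the reason. In Section 9.5.2 and the synopsis, label both duration endpoints as time on the maximum tolerated dose within the 12-month observation period. As an optional descriptor, report the number of patients still on the maximum dose at month 12.

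The cost is a little more chart abstraction for MRA users and one amended eDCF row; no more patients are needed. Some stops may still be undated where primary care information is absent from hospital records, and these would then be visible as not known. The change is cheapest before data collection ends (planned for July 2018 in Table 4). After that, recovering MRA stops means going back to the charts.

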10.1 Database management

pH Associates will be responsible for data management in this study, including quality checking of the data. The eDCF will be developed from a paper draft and then converted to electronic form in MACRO, which is a data management system that has a secure web-based data entry interface and is fully validated and compliant with Food and Drug Administration (FDA) Information Governance standard 21 CFR part 11 and Good Clinical Practice (GCP). The MACRO system has restricted access permissions for data entry and data management and it maintains a visible audit trail of all changes to data and activity in the system in line with 21 CFR part 11. It has been widely used in the UK NHS for complex interventional clinical trials. It is used by pH Associates on a range of real world evidence studies.

All electronic study data will be securely stored on a password-protected internal, UK-based server at the pH Associates office and all study related documents will be kept in a locked cupboard when not in use. Entry to the study database will be restricted (by password protection) to only those pH Associates staff members directly involved with the study. System backups for data stored at pH Associates and records retention for the study data will be consistent with pH Associates standard procedures.

10.2 Data quality checks

Data collection will be completed by trained staff either from pH Associates or the NHS care team at study centres. All data collectors will be provided with Data Collection Guidelines to support consistent completion of eDCFs. Additionally, the same data collector will be used at each centre, wherever possible. Data entered into eDCFs will be validated at the point of entry into MACRO using criteria to be pre-agreed criteria with Vifor Fresenius Medical Care Renal Pharma UK Ltd before the start of data collection. All data received by pH Associates will be checked for participant eligibility, accuracy and completeness using programmed validation checks, in accordance with the agreed data management plan.

Furthermore, the accuracy and quality of data collection will be monitored by the completion of source data verification (SDV) for 10% of eDCFs at each centre by pH Associates staff. SDV will only be possible for secondary care data. SDV will not be conducted for primary care prescribing and test results data as access to source GP records will not be sought. Where data collection is completed by pH Associates staff, the staff member who carries out the SDV will be different to the person responsible for data collection at that specific centre. Remedial training will be given to data collectors if necessary.

Quantitative data collected for laboratory (haematology and biochemistry) parameters will be standardised per centre using laboratory reference ranges entered on the eDCF. This will allow pooling of these study parameters across centres. Data submitted to the study will be checked for completeness and queries will be raised by the pH Associates data management

team. Study centres will be required to co-operate with the data management team in the resolution of these queries. Where data queries are raised by the pH Associates data management team, study centres will be required to cooperate with pH Associates in the resolution of these queries. On completion of the first three eDCFs from at least two centres, a pilot of the data collection process will be completed. This will assess the feasibility of capturing the study dataset using the eDCF, confirm that data collection can be achieved efficiently, and also establish that the data collection method is suitably robust.

11. Study sample size

Given the descriptive nature of this study, a preliminary estimation of the required sample size is expressed in terms of precision and not statistical power. It is expected that approximately 100 patients will be sufficient to generate reliable results, as determined by relatively narrow confidence intervals.

Table 3 Confidence limits for different sample sizes and mean doses of RAASi achieved

Mean dose (as % of target dose)	50 patients		100 patients		150 patients	
	LCL	UCL	LCL	UCL	LCL	UCL
90%	82%	98%	84%	96%	85%	95%
80%	72%	88%	75%	85%	76%	84%
70%	63%	77%	65%	75%	66%	74%
60%	54%	66%	56%	64%	57%	63%
50%	45%	55%	47%	53%	47%	53%
40%	34%	46%	36%	44%	37%	42%
30%	23%	37%	25%	35%	26%	32%

LCL – lower confidence limit

UCL – upper confidence limit

The table shows that the reliability of estimates for the mean dose of RAASi achieved (as a percentage of the target dose) improves when the study sample is increased from 50 to 100

patients. This is applicable for relatively small or large percentages of the target dose achieved. Reliability does not improve much more when the sample size is increased from 100 to 150 patients. Therefore, approximately 100 patients will be sufficient to generate reliable results for the primary endpoint. The number of patients in the study will be allocated as follows: 50% (approximately n=50) with CKD and HF and 50% (approximately n=50) with CKD and T2DM. This distribution includes patients with all three conditions: CKD, HF and T2DM.

12. Statistical analysis

Analyses will be performed by pH Associates. Data from all centres will be pooled for analysis. Distributions and descriptive statistics of central tendency (medians and arithmetic means) and dispersion (standard deviation, interquartile range) will be presented for quantitative variables wherever possible. Categorical variables will be described with frequencies and percentages. Ordinal variables will also have medians and interquartile ranges described. 95% confidence intervals will be presented for estimates of proportions and means of distributions.

Between-group differences (for drug type and patient group) will be evaluated by unpaired t-tests, Wilcoxon rank-sum test or chi-square test, as appropriate. Within-group differences will be assessed by paired sample t-test, Wilcoxon matched-pairs signed-ranks test or McNemar test, as appropriate. 95% confidence intervals will be presented for estimates of proportions and means of distributions, as appropriate. Additional statistical tests may be applied, as appropriate to the data. Statistical analyses will be carried out using Stata version 14 (StataCorp LLC) and Microsoft Excel™ 2010. A technical overview of study reporting will be provided in a statistical analysis plan (SAP) before data collection is completed.

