7.3 Secondary objectives

1. To describe doses of MRA prescribed to patients with CKD and HF
2. To describe other drug types concomitantly prescribed for CKD and/or HF in patients treated with RAASi
3. To describe clinical outcomes associated with RAASi treatment
4. To describe the demographic and clinical characteristics of patients treated with RAASi who do not achieve target dose, at initiation of treatment

8. Hypothesis

This is a descriptive study and therefore an a priori hypothesis will not be tested.

9. Study design and methodology

The study is designed and will be conducted according to the requirements of the European Network of Centres for Pharmacoepidemiology and Pharmacovigilance (ENCePP) and International Society for Pharmacoepidemiology (ISPE) guidance, as appropriate^{10,11}. This will be a multi-centre, retrospective non-interventional study of patients with CKD and HF

and/or T2DM. The study will take place in between five and ten NHS secondary care centres in the UK.

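### Section 10.2 standardises every laboratory value to the centre's reference range without exempting serum potassium, whose endpoints use fixed mmol/L cut-offs

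*Protocol*

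**What the plan says.** Section 10.2 (Data quality checks) sets one rule for all quantitative haematology and biochemistry data: they will be "standardised per centre using laboratory reference ranges entered on the eDCF". It gives the purpose in the next sentence: "This will allow pooling of these study parameters across centres". It gives no formula and names no parameter as exempt.

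The synopsis (Section 4, endpoints 7 and 8) and Section 9.5.2 define two hyperkalaemia endpoints by absolute concentrations. The first is "Proportion of patients with elevated serum potassium level (>5.1 mmol/L, >5.5 mmol/L or >6.0 mmol/L) during the observation period". The second counts episodes per patient at the same three cut-offs. Endpoints 9 and 10 are the changes in mean serum potassium and creatinine from index date to last result; no unit is given for these two.

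Table 2 in Section 9.5.3 lists what is collected for potassium and creatinine: "Date of observation, level". The measured value is therefore on file. On the number of sites, Section 9 says: "The study will take place in between five and ten NHS secondary care centres in the UK". Section 12 pools all centres and does not mention standardised laboratory values.

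**The concern.** Bringing results to common units does not require a reference range. A rule that works centre by centre, uses the local reference range and aims at pooling reads most naturally as an adjustment of the values themselves. Potassium is a biochemistry parameter, so the rule covers it. A potassium value adjusted in this way cannot be compared with 5.1, 5.5 or 6.0 mmol/L unless all centres share the same range.

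If the rule were carried through to the endpoints, a patient's hyperkalaemia status would depend on the local laboratory's range as well as on the measured potassium. Changes in potassium and creatinine would be stretched or shrunk by a factor specific to the centre. Section 12 also compares drug types and patient groups, so range differences could enter those comparisons if the groups are unevenly spread over centres. Section 6 gives hyperkalaemia, actual or feared, as a reason why patients miss target dose, so these endpoints bear directly on the study's rationale.

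**Working it through.** The protocol gives no figure for these endpoints to reproduce. What follows shows what the rule could do under stated assumptions.

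**From the protocol:** cut-offs of 5.1, 5.5 and 6.0 mmol/L (Section 9.5.2); five to ten centres (Section 9); standardisation by local range (Section 10.2).

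**Assumed, not in the protocol:** the reference ranges, a linear mapping, and the potassium distributions.

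**1. Mapping.** A value x from a centre with range (lo, hi), put on a common range (LO, HI), becomes

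x' = LO + (x − lo)(HI − LO)/(hi − lo).

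The measured value that lands on a cut-off t is

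x = lo + (t − LO)(hi − lo)/(HI − LO).

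**2. Two ranges, 3.5-5.0 and 3.5-5.3 mmol/L (widths 1.5 and 1.8).**

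- Centre with 3.5-5.0 mapped to 3.5-5.3: the measured value equivalent to 5.5 is 3.5 + 2.0 × 1.5/1.8 = 5.17. A measured 5.2 becomes 3.5 + 1.7 × 1.8/1.5 = 5.54 and would count as above 5.5.
- Centre with 3.5-5.3 mapped to 3.5-5.0: the measured value equivalent to 5.5 is 3.5 + 2.0 × 1.8/1.5 = 5.90. A measured 5.6 becomes 3.5 + 2.1 × 1.5/1.8 = 5.25 and would no longer count.
- A within-patient potassium change is multiplied by 1.8/1.5 = 1.20 in the first case and by 1.5/1.8 = 0.83 in the second. A creatinine change would likewise be multiplied by the ratio of the creatinine range widths.

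**3. Share of patients above 5.5, with highest potassium N(5.1, 0.5).**

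- Measured values: P(Z > (5.5 − 5.1)/0.5 = 0.80) = 21.2%.
- Effective cut-off 5.17: P(Z > 0.13) = 44.7%.
- Effective cut-off 5.90: P(Z > 1.60) = 5.5%.

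The last two apply only at the rescaled centre. Pooled in equal numbers with a centre that is unchanged:

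- (44.7 + 21.2)/2 = 33%
- (5.5 + 21.2)/2 = 13%

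**4. Sensitivity to the assumed range.** Common range 3.5-5.3; readings N(4.8, 0.5); on measured values 8.1% exceed 5.5.

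| Centre range (mmol/L) | Measured value equivalent to 5.5 | Readings flagged >5.5 |
|---|---|---|
| 3.5-5.3 | 5.50 | 8.1% |
| 3.3-5.3 | 5.52 | 7.4% |
| 3.6-5.2 | 5.38 | 12.4% |
| 3.5-5.1 | 5.28 | 17.0% |
| 3.5-5.0 | 5.17 | 23.2% |
| 3.4-5.5 | 5.73 | 3.1% |

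For assumed means from 4.6 to 5.0, the share on measured values runs from 3.6% to 15.9%; at the 3.5-5.0 centre it becomes 12.9% to 36.9%.

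**5. A unit-free scale does not help.** As a fraction of the range, 5.5 mmol/L is (5.5 − 3.5)/1.5 = 1.33 for 3.5-5.0 and (5.5 − 3.4)/2.1 = 1.00 for 3.4-5.5. No single standardised value corresponds to the cut-off.

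With measured values in mmol/L, the cut-offs stay at 5.1, 5.5 and 6.0 at every centre and this source of error disappears.

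**The case against.** A reader might infer that the plan will misclassify hyperkalaemia. The protocol does not support that. It leaves the standardisation undefined and never says that a transformed value replaces the measured one. The rule sits under data quality checks, and the analysis section does not refer to it. Table 2 keeps the measured level, and the mmol/L in endpoints 7 and 8 points towards measured values. The agreed data management plan or the SAP, neither of which is at hand, may settle the scale. All of this stands, and it makes the consequence conditional.

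Two further inferences fail. Endpoints 9 and 10 state no unit, so the text does not contradict itself on those changes; they would be affected only if standardised values were used. Nor are 45% and 5.5% study-level results: they hold at one rescaled centre under assumed inputs, and across five to ten centres errors could partly offset. The primary endpoint, RAASi dose as a percentage of target, is untouched.

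The objection does not remove the conflict. Section 10.2 states a rule rather than leaving a detail open. The rule covers potassium, and nothing in the protocol says the endpoints use unscaled values. If only unit conversion was meant, the sentence names the wrong tool and still needs correcting.

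**Conclusion.** The point holds as an unreconciled conflict between a blanket data-handling rule and two secondary endpoints defined by fixed concentrations. Misclassification could follow, but only if the cut-offs are applied to range-standardised values and the centres' ranges differ. The protocol states neither condition. In the examples, the effect runs from none (matching ranges) or nearly none (8.1% to 7.4%) to more than a doubling of the share above 5.5 mmol/L at a single centre, and it can go either way. All of these sizes rest on assumed ranges, a linear mapping and normal distributions. The sponsor should correct the text, because followed literally it makes hyperkalaemia status depend on the local range.

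**What to change.** Amend the sentence in Section 10.2 to say that laboratory values are converted to common units (for example potassium in mmol/L and creatinine in µmol/L), and that the three potassium thresholds and the potassium and creatinine change endpoints use the measured values in those units. State that reference-range standardisation is not applied to these endpoints. Local ranges may still serve for data checks, or for other parameters where needed.

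The cost is a one-sentence amendment, with the data management plan brought into line. No additional data are required, since the measured levels are already collected.
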